In the first three months (the Observation phase) of this proof-of-concept study, a telemedicine center for the PACU will monitor patients assigned to two PACU bays. Both the telemedicine center and nurses caring for patients in the PACU bays will separately document physiological derangements (Table 2), treatable symptoms (Table 3), or a situation requiring urgent medical intervention (telemedicine center only; Table 4) during the PACU stay. Clinicians in the telemedicine center will assess when the patient meets discharge criteria, based on the modified Aldrete scale¹⁵ and their clinical judgment. They will document the time that discharge criteria are met, the modified Aldrete scale score at this time, and any additional relevant information. If clinicians in the telemedicine center judge that they are unable to determine a patient's readiness for discharge, they will document their reasons (Table 5). Clinical judgment will be used in determining appropriate discharge parameters for patients with pre-existing conditions. The telemedicine center clinicians will document each patient's information outlined in Tables 2-5 directly into REDCapTM (a secure web application for managing online surveys and databases) and AlertWatch. After a patient has been discharged from the PACU, the PACU nurse will fill out a form providing information outlined in Tables 2-5. This includes

information on physiological derangements, treatable symptoms, and discharge information. This form will be collected by the research team, and the information in the form will be documented in REDCap. During this phase of the study, clinicians in the telemedicine center will not communicate with clinicians in the PACU (nurses or physicians), unless there is a patient safety event.

Table 2. Physiological derangements and complications

Did the patient have any of the following physiological derangements:	Definition: (for study purposes)
Persistent confusion / delirium	
Tachycardia	HR >120/min
Bradycardia	HR <45/min
New onset atrial fibrillation	
Respiratory depression	<8 respirations per minute
Hypoxemia	<90% O ₂ Saturation
Hypotension	MAP <55
Weakness	<5/5 power in limbs
Emesis / vomiting	
Hyperglycemia	Glucose >200mg/dL
Hypothermia	Temperature < 35.5 C
Low urine output (for PACU stay >4h)	<0.5 ml/kg per hour

Table 3. Symptoms requiring treatment

Did the patient complain of the following symptoms:	
Dizziness or lightheadedness	Difficulty breathing
Nausea	Shivering

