Severe pain (Numerical Rating Scale >7/10)	Itching
Chest pain unrelated to surgery	

Table 4. Emergency medical interventions

Did the telemedicine center contact PACU clinicians for any of the following interventions:	
Intubation	Unplanned transfusion
Assisted ventilation	Naloxone administration
Cardiopulmonary resuscitation	Return to OR
Cardioversion	Other (free text box)
If Yes, please check all that apply:	
 PACU nurse already aware of the situation	
 PACU nurse unaware of the situation	
 PACU nurse disagreed with the assessment	
 PACU nurse had already spoken to the supervising physician regarding the situation	

Other (please describe):

*Only the telemedicine center will document the detection of urgent situations.

Table 5. Patient discharge readiness

At what time did the patient sufficiently recover to be discharged (case attending anesthesiologist contacted for discharge)?	
PACU Nurses	Telemedicine Center for PACU
Time anesthesiologist is contacted for discharge evaluation	Time ready for discharge
Aldrete Score at discharge	Aldrete Score at discharge
	Unable to determine patient's readiness for discharge
Modified Aldrete Scale Component and Scoring Parameters	If Unable to fully assess, select reason(s) why (Checkbox)
Respiration	 More patient information needed  Equipment issues  Patient cooperation  Other (free text box)
2 – Able to take deep breath and cough	
1 – Dyspnea / Shallow Breathing	
0 – Apnea	
O₂ Saturation	
2 – Maintains > 92% on room air	
1 – Needs O ₂ inhalation to maintain O ₂ saturation > 90%	
0 – Saturation <90% even with supplemental O ₂	
Consciousness	
2 – Fully awake	
1 – Arousable on calling	
0 – Not responding	
Circulation	
2 – BP ± 20mmHg pre-op	
1 – BP ± 20-50mmHg pre-op	
0 – BP ± greater than 50mmHg pre-op	
Motor Activity	
2 – Able to move 4 extremities voluntarily or on command	
1 – Able to move 2 extremities voluntarily or on command	
0 – Able to move 0 extremities voluntarily or on command	

Interaction Phase (3 months)

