Physiological derangements – Success will be measured (in the observation phase) by the ability of the telemedicine center clinicians to identify physiological derangements as they are occurring in the PACU. The extent to which the telemedicine center clinicians can identify these physiological derangements will be measured by comparing PACU nurse and telemedicine center assessment surveys for each patient (Figure 3).

Symptom identification and management – Success will be measured (in the observation phase) by the ability of the telemedicine center clinicians to identify treatable symptoms as they arise in the PACU. The extent to which the telemedicine center clinicians can identify these treatable symptoms will be measured by comparing PACU nurse and telemedicine center assessment surveys for each patient (Figure 3).

Emergency situations – Success will be measured (in the observation phase) by the ability of the telemedicine center clinicians to identify situations requiring emergency medical intervention as they are occurring in the PACU. By construction, any time the telemedicine center feels that an emergency situation is present, preserving patient safety mandates contacting the bedside clinician.

During each such contact, the telemedicine center clinician will ask if the PACU nurse was already aware of the situation, disagreed with the assessment, and had already spoken to the supervising physician regarding it. The occurrence of emergency medical situations will be extracted from the electronic health record, and the agreement between telemedicine center and PACU nurse assessments will be quantitated.

PACU discharge – Success will be measured by the ability of the telemedicine center clinicians to identify when patients are ready for discharge (observation phase [without communication] and interaction phase [active communication with patient and PACU clinicians]) (Figure 3). The impact of the telemedicine center on this key function will be examined based on feedback from key stakeholder focus groups (interaction phase; see *Aim 2*). The difference between sign-out times in the observation and the interaction phases will be compared.

Data collection methods and measures during the interaction phase

Aim 1: Demonstrate the potential utility of a telemedicine center for the PACU, to assist with PACU functions

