The accuracy of physiologic, symptom, and status assessments is less straightforward to analyze. At the heart of the proposal is the belief that telemedicine assistance will detect some abnormalities not caught (or caught later) by the bedside team and detect that the patient has adequate status for PACU discharge before the bedside nurse. Using the bedside assessment as a gold standard is therefore limited. Similarly, although we believe that abnormalities detected by either bedside or telemedicine are unlikely to be false positives, we have no way of assuring that. We also cannot reliably determine the timing of the bedside nurse's detection of an abnormality, as they may document it much later if they believe it does not require an immediate intervention.

Each status assessment event can occur multiple times for each patient; however, we are unlikely to accurately capture the bedside nurse's impression of the number of times an event occurred. We will therefore binarize the presence of each assessment type and display confusion matrices (count tabulations) for each assessment type, which we will summarize with Jaccard indices. The "null hypothesis" that these measures do not agree at all is not meaningful or the subject of this study. As described above, neither is a directional superiority hypothesis possible to evaluate. Final Aldrete scores will be assessed with pearson correlation, and a t-test of the difference in scores presented. Differences in ready-for-discharge times will be summarized as mean and standard deviation, with the null hypothesis of zero mean tested by t-test with a robust standard error.

Agreement of emergency medical status is unlikely to have enough events to be statistically compared. We will present cross-tabulations of (emergency detected by telemedicine center:

yes/no) and (PACU nurse: disagree, investigate and agree, already aware, physician contacted). The absolute rate of telemedicine center false positives (team disagrees), true positives (team unaware), true positives (team aware), and false negatives (team aware > 15 minutes prior or t never detects) will be presented with 95% confidence intervals.

Data Collection

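### Tables 2 and 3 give telemedicine no 'could not assess' answer, so an item it could not examine cannot be told apart from one it missed

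*Combined protocol and SAP*

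**What the plan says.** The success measure for symptoms reads "Success will be measured (in the observation phase) by the ability of the telemedicine center clinicians to identify treatable symptoms as they arise". The measure for derangements is built the same way. Both compare the nurse's and the telemedicine center's surveys patient by patient.

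What telemedicine may do in that phase is spread over several sections. Under Observation Phase, the explicit ban on contact names PACU nurses and physicians and does not mention patients. The PACU discharge success measure contrasts "observation phase [without communication] and interaction phase [active communication with patient and PACU clinicians". Primary Intervention places two-way video in the interaction phase, and Interaction Phase is where contact with patients begins.

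Table 2 asks "Did the patient have any of the following physiological derangements" and includes weakness, defined as "<5/5 power in limbs". Table 3 asks "Did the patient complain of the following symptoms" and includes "Severe pain (Numerical Rating Scale >7/10". Neither table shows an answer for an item that could not be assessed. Table 5 does, for telemedicine only: "Unable to determine patient's readiness for discharge", with boxes for missing information, equipment, patient cooperation and other reasons. Observation Phase asks for reasons only for discharge readiness. A broader note about being unable to assess a patient's status appears under Interaction Phase and is also recorded in Table 5.

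For analysis, Secondary Outcomes says "We will therefore binarize the presence of each assessment type", then plans a count table per assessment type, summarized by Jaccard indices. It names no third category and no rule for items left unassessed.

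**The concern.** The nurse-yes, telemedicine-no cell can arise in two ways. Telemedicine may have had the information and overlooked the event, or it may have had no usable view of it. The first bears on the clinicians' ability to detect. The second bears on silent remote monitoring as a set-up, and may ease once telemedicine can speak with patients. The forms as printed do not record which occurred.

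For a proof of concept the distinction matters. A low index for an item could argue against the concept, or only for giving telemedicine a voice, and those lead to different next studies. The authors allowed for failed remote assessment in Table 5 but did not carry this over to the items on which Aims 1a and 1b rest.

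**Working it through.** The plan gives no figure on this point. Its only power statement concerns the primary outcome and is not involved. The check sets the sections side by side and then illustrates the size on assumed inputs.

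**Which items are exposed**

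| Items | Sources open to a silent observer | Exposure |
|---|---|---|
| Heart rate, saturation, pressure, respiratory rate | Waveforms, record | Little |
| Complaints: nausea, itching, dizziness, chest pain | Microphone, video, record | Partial |
| Limb power, confusion, numerical pain score | Mainly the nurse's examination or questions, if heard or charted | Most |

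Periods without usable audio, video or record data add to the exposure of any item that depends on them. The record is an imperfect substitute for asking, since Secondary Outcomes accepts that nurses may chart an abnormality much later.

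**Where an unassessed item falls**

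With present/absent coding and no third category, a telemedicine non-report is a 'no' by default.
- Nurse yes: it joins the nurse-only cell, together with true misses.
- Nurse no: it joins the both-absent cell. The Jaccard index ignores that cell, but the count table then shows agreement that nobody assessed.

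**Size, on assumed inputs**

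N = 250 patients (the plan's estimate per phase). Assumed: p = share the nurse marks present; u = share telemedicine cannot assess, unrelated to nurse status; s = detection when assessable; f = telemedicine-only reports among assessable nurse-negative patients.

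- Both = N·p·(1−u)·s
- Nurse only = N·p·(1−u)·(1−s) + N·p·u
- Telemedicine only = N·(1−p)·(1−u)·f
- Jaccard = both / (both + nurse only + telemedicine only)

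Excluding unassessable items drops the N·p·u term.

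*Case A: s = 1, f = 0.* Jaccard = 1−u, whatever p is. With p = 20% and u = 40%, both = 250 × 0.2 × 0.6 = 30 and nurse only = 250 × 0.2 × 0.4 = 20, so 30/50 = 0.60. With exclusion it is 30/30 = 1.00.

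*Case B: s = 0.8, f = 0.05, p = 20%.* With u = 40%, both = 24, nurse only = 6 + 20 = 26, telemedicine only = 6, so 24/56 = 0.43. With exclusion it is 24/36 = 0.67.

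| u | A, counted 'no' | A, excluded | B, counted 'no' | B, excluded |
|---|---|---|---|---|
| 20% | 0.80 | 1.00 | 0.55 | 0.67 |
| 40% | 0.60 | 1.00 | 0.43 | 0.67 |
| 60% | 0.40 | 1.00 | 0.30 | 0.67 |

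In case B at u = 40%, moving p from 10% to 30% gives 0.38 to 0.45 counted 'no', against 0.55 to 0.72 excluded.

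**The case against.** A reader might infer that the plan codes unassessable items as failures to detect. It does not say so. Binarization is introduced because events can recur and the nurse's count of them is unreliable, so it collapses repeats to ever or never. What stands is that no rule covers unassessed items and no category holds them.

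A reader might also infer that telemedicine had no means of knowing about symptoms. That goes too far. Table 3 asks about complaints, the bays have a microphone and camera, and telemedicine receives the record. A complaint made to the nurse can be heard or read. This narrows the concern to the items and periods named above. Silence toward patients is itself an inference, since the explicit ban names clinicians.

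Other objections carry weight:
- What silent monitoring fails to capture is a legitimate part of what the success measures ask.
- Secondary Outcomes limits the nurse record as a gold standard and sets no directional hypothesis, so the cell is formally a disagreement. It reads as a failure to identify only through the success measures.
- The cause is not wholly lost. Tables are given per assessment type, and telemedicine keeps documenting the same items in the interaction phase, so its reporting rates with and without patient contact could be compared. That comparison is confounded by period and by the merging of the two teams, and it does not classify individual patients.
- The actual forms are not in the document (Supplementary material is a placeholder), so the database may already hold such an option. The analysis text would then still need a rule for it.

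**Conclusion.** The point holds in a limited form. As printed, the forms and the analysis cannot separate 'could not examine' from 'missed' when the nurse marks an item present. The effect is concentrated in limb power, confusion, the numerical pain score and spells without usable data. Vital-sign items are largely untouched.

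The size is unknown. The values of u, p, s and f above are assumptions, and the documents offer nothing to fix them. The firm result is conditional: with perfect detection of assessable items and no extra reports, the index equals the assessable share.

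These are secondary, descriptive results with no success threshold, and the primary outcome and sample size do not depend on them. The change is still worth making, because it alters what Aims 1a and 1b can conclude.

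**What to change.** 1. Add a telemedicine response 'could not assess remotely' to each Table 2 and Table 3 item, with the Table 5 reason boxes. For complaint items, allow it only when the patient could not be heard or seen or the record was unavailable. Otherwise an unheard complaint and an absent one cannot be separated.
2. Report how often the response is used, per item.
3. Show telemedicine (yes / no / could not assess) by nurse (yes / no) for each item.
4. Give the Jaccard index and the share of nurse-reported events detected in two ways. The main figure includes all patients and counts 'could not assess' as not detected. The supplement excludes unassessable items.
5. State this coding in Secondary Outcomes.

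The cost is one more response per item and a slightly longer form. The assessable denominator is self-declared and could flatter detection if the response is overused; keeping the all-patients result as the main figure guards against that.

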After the completion of the hand-off procedure, the PACU nurse who interacted with the telemedicine center clinicians will complete a short survey to assess the telemedicine center's involvement in that patient's transfer of care.

The successful integration of the telemedicine center clinicians' hand-off activity will be measured in the following way:

Hand-off activity – Success will be measured (in the interaction phase) by the ability of the telemedicine center clinicians to join and contribute meaningfully to the hand-off discussion. The impact of the telemedicine center clinicians on this key function will be determined from feedback from key stakeholder focus groups (see *Aim 2*) and PACU nurse surveys. These stakeholders will comment on utility of the telemedicine center's involvement and provide suggestions for improvement. A binary assessment of hand-off

adequacy will be provided by the PACU nurse hand-off survey. The telemedicine center clinician will use a hand-off content checklist to record the number of mandatory items not discussed and number of recommended non-mandatory items discussed. For each of the observation and intervention phase, for 50 randomly selected cases a trained observer (not the participant in hand-off) will use the hand-off communication assessment tool of Weinger and others¹⁶ substituting the telemedicine center hand-off content checklist. A run-in phase of 1 month during the intervention will elapse before any of the 50 detailed communication evaluations are performed.

Aim 2 – Identify barriers to and facilitators for the implementation of a telemedicine center for the PACU, as perceived by key stakeholders

We will assess the attitudes of key stakeholders in order to identify barriers to and facilitators for implementation of a telemedicine center for the PACU. (Figure 3)

Stakeholder Focus Groups

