Contemporaneous control patients will also be gathered. A propensity score for study inclusion will be generated as a function of (minimally) surgery performed, calendar time, time of day, age, and sex. 3:1 matched control patients will be included. Differences will be analyzed by t-tests using permutation calibration. Confidence intervals on the difference in mean time to discharge readiness will be generated by nonparametric bootstrap. We will include a sensitivity

analysis where the interrupted time series method includes historical and contemporaneous control patients with the treatment indicator T for study patients,

$$Y_i = f_1(t_i)I(t_i < t_0) + f_2(t_i)I(t_i \geq t_0) + X_i\beta + T_i + \epsilon.$$

Based on data from our EHR, patients are currently in PACU for a mean of 150 min (standard deviation = 65 min) before they are determined to be suitable for discharge. Based on these values, with 250 patients in each phase (observation and interaction), this observational before and after study will have >70% power with an alpha <0.005 and > 90% power with an alpha <0.05 to detect a mean decrease in 20 min (from 150 min to 130 min) to PACU discharge readiness time. Statistical testing will be with appropriate statistical software. Using non-parametric bootstrap of historical data and a 3:1 control sampling ratio, the average standard error on the difference in means under the null hypothesis was 5.5 minutes, giving an anticipated 95% confidence interval width of 22 minutes. A somewhat larger standard error will be encountered when adjusting for covariates or secular trends; however, this suggests that we will be able to resolve differences in PACU readiness times of 20-25 minutes. This difference of approximately a third a standard deviation is usually regarded as a “small-moderate” sized effect.

Secondary Outcomes

Hand-off quality assessment from the PACU nurse binary survey response will be analyzed using a logistic regression model adjusting for surgical service, age, and sex. Because observation resources are required for hand-off evaluations, no matching will be performed, and no contemporaneous controls will be gathered. Adjusted differences in rates of inadequate hand-off will be summarized with 95% confidence intervals and model-based p-values.

Observed reported hand-off communication quality will be presented as a purely descriptive result.

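### The only hand-off measure with a planned test is a yes/no nurse rating, which cannot register improvement among hand-offs already rated adequate; a five-level item with a pre-fixed cut would add that at little cost

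*Combined protocol and SAP*

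**What the plan says.** The Hand-off Activity section counts the hand-off work as a success if telemedicine clinicians can join and "contribute meaningfully to the hand-off discussion". Four sources bear on this:

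- **Nurse survey.** A binary rating of hand-off "adequacy will be provided by the PACU nurse hand-off survey".
- **Content checklist.** The telemedicine clinician will "record the number of mandatory items not discussed and number of recommended non-mandatory items discussed".
- **Trained observer.** A published communication tool is applied to 50 randomly selected cases per phase.
- **Stakeholder focus groups.** These give comments on usefulness and suggestions for improvement.

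Under Statistical Methods, Secondary Outcomes, only the first source is tested: "Hand-off quality assessment from the PACU nurse binary survey response will be analyzed using a logistic regression model adjusting for surgical service, age, and sex". The output is specified as follows: "Adjusted differences in rates of inadequate hand-off will be summarized with 95% confidence intervals and model-based p-values". For the observer tool, "Observed reported hand-off communication quality will be presented as a purely descriptive result". No analysis is stated for the checklist counts.

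No reason is given for using two levels. The same section does give a reason for reducing the derangement and symptom assessments to present/absent: the bedside count of events is unreliable. That reason does not apply to a single nurse rating.

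**The concern.** Hand-off quality is a matter of degree. The telemedicine clinicians are to join the conversation and supply relevant missing information, and nothing limits this to hand-offs that would otherwise have been judged inadequate. When an acceptable hand-off becomes a good one, the yes/no answer stays the same and the planned test sees nothing.

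If most hand-offs are rated adequate, the comparison rests on the few that are not. A null result could then mean either that telemedicine contributed nothing or that it improved hand-offs that were already acceptable. The test cannot tell these apart, and a yes/no answer cannot be expanded into grades afterwards.

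**Working it through.** **The plan's own figure.** The only power statement concerns time to discharge readiness: 250 per phase, SD 65 min, difference 20 min. SE = 65 × √(2/250) = 5.81, and 20/5.81 = 3.44. Two-sided power is Φ(3.44 − 1.96) = 93% at alpha 0.05 and Φ(3.44 − 2.81) = 74% at alpha 0.005. The stated values (over 90% and over 70%) reproduce. No power is stated for hand-off.

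**Inputs for hand-off.** From the documents: 250 patients per phase, no matching, no contemporaneous controls. Assumed, because the documents are silent: one survey per patient in both phases, independent ratings, two-sided alpha 0.05, five levels from worst to best, levels 1-2 inadequate, and the rating distributions and effects below.

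**Formulas (unadjusted).**
- Binary: power = Φ[(|p₁ − p₂| − 1.96·SE₀)/SE₁], with SE₀ from the pooled proportion and SE₁ from the separate proportions.
- Five-level: tie-corrected Wilcoxon, the score test of the proportional-odds model. θ = Σ qₖ(Fₖ₋₁ + pₖ/2), where p and q are the observation- and interaction-phase level probabilities and F is the cumulative sum of p. SE₀ = √[(500/(12 × 250²)) × (1 − Σ π̄ₖ³)], where π̄ₖ is the average of pₖ and qₖ. Power ≈ Φ(|θ − 0.5|/SE₀ − 1.96) plus the opposite tail.

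**Case A: the whole scale shifts, odds ratio 0.6 for a worse rating.** Start from (.02, .08, .10, .20, .60).
- Binary: the odds 0.10/0.90 = 0.111 become 0.0667, so p₂ = 0.0625. SE₀ = SE₁ = 0.0244. (0.0375 − 0.0479)/0.0244 = −0.43, power about 34%.
- Five-level: q = (.012, .050, .068, .155, .714), θ = 0.560, SE₀ = 0.0218, z = 2.75, power Φ(0.79) = 79%.

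Simulation (20,000 replicates per row, 250 per phase unless stated):

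| Observation phase | Binary | Five-level |
|---|---|---|
| 10% inadequate, 60% in top level | 34% | 79% |
| 10% inadequate, 80% in top level | 33% | 56% |
| 20% inadequate | 55-56% | 79-85% |
| 30% inadequate | 69% | 89% |
| 50% inadequate | 81% | 89% |
| 10% inadequate, 125 per phase | 19% | 32-50% |

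**Case B: change wholly above the line** (up to 10 percentage points move from level 4 to level 5). The binary test keeps only its 5% error rate. The five-level test has 7% to 80% power, depending on the starting distribution.

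**Case C: rescue at the line** (half of the inadequate hand-offs move to level 3). Same start as Case A.
- Binary: 0.10 to 0.05. SE₀ = 0.0236, SE₁ = 0.0235. (0.050 − 0.0462)/0.0235 = 0.16, power about 57%.
- Five-level: q = (.01, .04, .15, .20, .60), θ = 0.505, SE₀ = 0.0227, z = 0.22, power 5-6%.
- At 20% inadequate: 89% against 9-10%.

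**Case D: effect strongest at the line and fading above it** (cumulative odds ratios 0.6, 0.6, 0.8, 0.9). At 10% inadequate, 33-34% binary against 9-14% five-level. At 50%, 81% against 67%. Binary leads in all seven distributions tried.

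**Clustering by nurse** lowers both powers. Illustration, all assumed: 25 ratings per nurse and intraclass correlation 0.05 give a design effect of 1 + 24 × 0.05 = 2.2, so 250/2.2 ≈ 114 effective surveys. At 20% inadequate and an odds ratio of 1.75 for a better rating, power falls from 62% to 33% (binary) and from 93% to 64% (five-level).

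**The case against.** A reader might infer that a five-level item is simply more powerful and that its common odds ratio should replace the binary test. The documents do not support that. The gain in Case A comes from assuming the same shift at every cut. The stated mechanism is supplying missing information, and the example given concerns insulin and glucose management in a patient with type I diabetes. That fits rescue of an inadequate hand-off at least as well, and Cases C and D show that the binary test then does better, often by a wide margin. The rate of inadequate hand-off is also a direct, readily understood target. This part of the objection stands and decides which analysis should lead.

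A reader might also infer that graded improvement is lost to the study, or that Aim 1e turns on this p-value. Neither follows. Checklist counts and observer ratings record graded change, and focus groups also inform the judgment. This is a secondary outcome of a proof-of-concept study.

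Two cautions remain. The survey form is not in the documents (Supplementary material holds a placeholder), so it may carry further items, although none is described or analysed. The nurses know the study phase, so a finer subjective scale could also pick up enthusiasm. None of this removes the narrower point: the one planned test cannot detect change within the adequate group, and no reason is given for collecting only two levels.

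**Conclusion.** The point holds as a cheap improvement to the plan and does not amount to an error in it. That the planned hand-off test cannot see improvement within the adequate group follows from the text alone.

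The size is conditional, because the documents give neither a rate of inadequate hand-off nor an effect shape. With 250 independent surveys per phase and a common odds ratio of 0.6, the five-level analysis gains about 8 points (50% inadequate) to 45 points (10% inadequate, 60% in the top level). Under rescue to level 3 at 10% inadequate, the binary test leads by about 50 points (57% against 5-6%). A five-level item with a fixed cut supports both analyses, so neither shape has to be bet on at the collection stage. The binary analysis should stay in the lead.

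**What to change.** **Hand-off Activity.** Replace the yes/no question with one five-level adequacy rating. Word the labels so that the boundary is explicit, with levels 1-2 fixed in advance as inadequate and 3-5 as adequate. State that the same item is completed in both phases. The section describes the survey for the nurse who interacted with the telemedicine clinicians and places success in the interaction phase, so collection in the observation phase should be spelled out.

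**Statistical Methods, Secondary Outcomes.** Keep the planned logistic regression and adjusted difference in "rates of inadequate hand-off" as the lead analysis, using the fixed cut. Add a prespecified proportional-odds regression on the five levels with the same covariates and a phase term, reporting the common odds ratio with its 95% confidence interval.

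**Cost.** One reworded item and a few sentences of text; no added patients, visits or staff. The downsides are a check of proportional odds, one more secondary p-value, and the chance that a cut on a five-level item does not match a direct yes/no answer exactly. The item must be settled before surveys begin.
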